Cover Page

Study Protocol

Project title: Genetic and risk factors in exfoliation glaucoma (Glaugene)

NCT: N.A.

Date of approval: 2012, May 6.

Summary and variable explanations

Project: Genetic and risk factors in exfoliation glaucoma (Glaugene)

Variables at inclusion:

- 1) Age: measured in years
- 2) Sex: female/male
- 3) Visual acuity: measured in Snellen's units (0.1-1.0)
- 4) Intraocular pressure (IOP): measured in mmHg, measured with applanation tonometer.
- 5) Central corneal thickness (CCT): measured with OCT, measured in μm
- 6) Visual field: performed using a Humphrey device, software 24-2 (SITA-fast). The variables included in the study are the mean deviation (MD) and the visual field index (VFI). The MD measured in dB, and the VFI measured in %.
- 7) Gonioscopy: performed in dark rum, classified the angle in 4-0 and pigmentation in 3-0.
- 8) The cup/disc ratio (CD ratio), measured with a 90-lins after dilation.
- 9) Cataract status measured as patient cataract operated or not (Yes/No).
- 10) Presence of glaucoma in one or both eyes.
- 11) Presence of exfoliation, measured after dilation. Classified as Yes/No.
- 12) Treatment with IOP lowering eye-drops: measured as the number of medicines and not the number of bottles.
- 13) Laser (SLT) treatment: measured as Yes/No.
- 14) At inclusion patients answered a questionnaire with several questions like how long they had glaucoma, diabetes, hypertension, smoking, family history for glaucoma, use of medicines, other eye diseases and other general diseases. Please see the questionnaire in a separate file.
- 15) Genetics were evaluated as allele's frequencies of the *LOXL1*_SNPs. Genetic analysis was performed at LGC Genomics (Hoddesdon, Herts, UK) using competitive allele-specific PCR (KASP) genotyping.

Variables at follow-up (three years) tested every six months:

- 1) Visual acuity: as above, see 3)
- 2) The IOP: as above see 4)
- 3) The visual field (MD and VFI), as above see 6)
- 4) Cataract operation: as above, see 9)
- 5) Number of medications: as above, see 12)
- 6) Laser treatment (SLT), as above, see 13)

Study Protocol

Inclusion

Patients' ID:

Protocol number:

Name and surname:

Date:

Age:

Sex:

	Right	Left
Visual acuity		
IOP		
CCT		
VF-MD		
VF-VFI		
Gonioscopy-angle		
Gonioscopy-pigment		
C/D Ratio		
Cataract operation		
Glaucoma		
Exfoliation		
Eye-drops		
SLT		

Additional information:

6 months Check-up

	Right	Left
Visual acuity		
IOP		
Visual field-MD		
Visual-field-VFI		
Cataract operation		
Number of medications		
SLT		

Additional information:

12 Months Check-up

	Right	Left
Visual acuity		
IOP		
Visual field-MD		
Visual-field-VFI		
Cataract operation		
Number of medications		
SLT		

Additional information:

18 Months Check-up

	Right	Left
Visual acuity		
IOP		
Visual field-MD		
Visual-field-VFI		
Cataract operation		
Number of medications		
SLT		

Additional information:

24 Months Check-up

	Right	Left
Visual acuity		
IOP		
Visual field-MD		
Visual-field-VFI		
Cataract operation		
Number of medications		
SLT		

Additional information:

30 Months Check-up

	Right	Left
Visual acuity		
IOP		
Visual field-MD		
Visual-field-VFI		
Cataract operation		
Number of medications		
SLT		

Additional information:

36 Months Check-up

	Right	Left
Visual acuity		
IOP		
Visual field-MD		
Visual-field-VFI		
Cataract operation		
Number of medications		
SLT		

Additional information:

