## Cover Page

Plan Statistical analysis

Project title: Genetic and risk factors in exfoliation glaucoma (Glaugene)

NCT: N.A.

Date of approval: 2012, May 6.

All statistical analyses will be performed using SPSS version 28.0.1.0 (IBM, [name]) software. Clinical characteristics of the cohort will be compared in relation to progression/no progression of glaucoma based on guided progression analysis (GPA). Categorical variables will be compared with Fisher's exact test while continuous variables with Student's t-test. The single nucleotide polymorphism (SNP) allele distribution between no progression and progression cases based on GPA will be compared using Fisher's exact test. The distribution of the haplotypes between no progression and progression cases based on GPA will be compared using Chi2 analyses within the Haplovie 4.1 software. The relation between the SNPs and progression/no progression in glaucoma will be tested using regression analyses (logistic or linear). In these analyses, mean deviation (MD) and visual field index (VFI), in addition to GPA, will be used as outcome variables measuring progression/no progression of glaucoma. Potential covariates will be first tested for association with the outcome variable (i.e., GPA, MD, and VFI) using univariate linear or logistic regression (depending on the character of the outcome variable). Associated variables will then be included as covariates in multivariate regression analyses. Finally, a regression analysis will be performed, including the genotypes of the two SNPs as predictors (both SNPs within the same model) and GPA/MD/VFI as outcome variables.

A power analysis based on Fisher's exact test will be performed using the Power and Sample Size Calculations software (<http://biostat.mc.vanderbilt.edu/PowerSampleSize>). Each SNP will be analysed separately. In all cases, the type I error ( $\alpha$  error) will be set to 0.05.

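### Inclusion IOP is analysed without corneal thickness, and the covariate rule can leave CCT out, so the IOP risk-factor association may be biased by an amount and in a direction the documents do not fix

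*Protocol*

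**What the plan says.** Protocol, Variables at inclusion, item 4: "Intraocular pressure (IOP): measured in mmHg, measured with applanation tonometer". No correction for corneal thickness is stated. Item 5: "Central corneal thickness (CCT): measured with OCT, measured in μm". The inclusion form has an IOP row and a CCT row for each eye. At follow-up IOP is repeated by the same method ("The IOP: as above see 4"), but CCT is not on the follow-up list.

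The SAP names neither IOP nor CCT, so both fall under its general rules:

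- Group comparison: "Clinical characteristics of the cohort will be compared in relation to progression/no progression of glaucoma based on guided progression analysis (GPA"), and then "Categorical variables will be compared with Fisher's exact test while continuous variables with Student's t-test".
- Covariate selection: "Potential covariates will be first tested for association with the outcome variable", one at a time by linear or logistic regression, and then "Associated variables will then be included as covariates in multivariate regression analyses".

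No covariate is forced into a model. Alpha is 0.05 throughout; no separate screening threshold is given.

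**The concern.** An applanation reading is taken by flattening the cornea, so it is reasonable to suppose that part of the reading reflects corneal thickness rather than pressure. If so, CCT is needed beside IOP to interpret IOP, whether or not CCT predicts progression.

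The SAP's entry rule asks a different question: does CCT predict the outcome by its own p-value? A variable that acts only by distorting another measurement will usually fail that test. The t-test and the univariate screen for IOP take no account of CCT at all. If CCT also bears on progression, the unadjusted IOP association mixes the two effects, and IOP may fail its own screen before CCT can be fitted beside it.

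At stake is the estimate for IOP as a risk factor, which the project title brings into scope. This is narrower than a general objection to univariate screening. It concerns one pair of measurements, both collected, where one may carry error that the other explains.

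**Working it through.** The plan gives no sample size, standard deviations, progression rate or IOP effect, so there is no figure of its own to reproduce. Every input here is assumed.

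**Inputs (binary GPA outcome).** 200 patients, 30% progress; true IOP SD 5 mmHg; CCT SD 35 µm, independent of true IOP; true OR 1.5 per 5 mmHg; reading = true IOP + b × CCT (centred), with b = 0.02, 0.04 or 0.07 mmHg/µm (0.2, 0.4 or 0.7 mmHg per 10 µm). The direct effect of CCT on the log odds is g per µm: zero, or ±ln(1.3)/35 = ±0.00750.

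**Formula.** To a linear approximation, the log-odds slope on the reading without CCT is

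(β × 25 + g × b × 1225) / (25 + b² × 1225), with β = ln(1.5)/5 = 0.0811, so β × 25 = 2.027.

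The denominators are 25.49, 26.96 and 31.00 for the three shifts. The OR per 5 mmHg is exp(5 × slope).

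- CCT unrelated to progression (g = 0): slopes 0.0795, 0.0752, 0.0654; OR **1.49, 1.46, 1.39**.
- Thin corneas at higher risk (g = −0.00750): numerators 1.844, 1.660, 1.385; slopes 0.0723, 0.0616, 0.0447; OR **1.44, 1.36, 1.25**.
- Thick corneas at higher risk (g = +0.00750): numerators 2.211, 2.395, 2.670; slopes 0.0867, 0.0888, 0.0861; OR **1.54, 1.56, 1.54**.

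**Simulation with the same inputs** (1,500 cohorts per setting; shifts 0.2 / 0.4 / 0.7). Repeated runs agreed to within about five points of power.

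| Role of CCT | OR, IOP alone | OR, IOP + CCT | Power, t-test | Power, IOP + CCT | CCT passes its screen |
|---|---|---|---|---|---|
| Reading only | 1.50 / 1.45 / 1.39 | 1.50-1.51 | 71 / 68 / 64% | 70-72% | about 5% |
| Thin cornea, OR 1.3 per SD | 1.43 / 1.35 / 1.24 | 1.51-1.52 | 63 / 51 / 33% | 72 / 72 / 71% | 39 / 40 / 39% |
| Thick cornea, OR 1.3 per SD | 1.54-1.57 | 1.51-1.52 | 79-85% | 71-74% | not tabulated |

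The 5% in the first row follows from the set-up: an unassociated variable passes a 5% test 5% of the time. It shows what the rule does; it is not separate evidence.

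**The SAP's two-step rule** (screen IOP and CCT, fit both if both pass), in the thin-cornea setting: IOP is found in 62% down to 32% of cohorts as the shift grows, against about 71-74% when CCT is always included. The later multivariable step does not recover what the IOP screen loses.

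**Sensitivity to the spreads.** With CCT unrelated to progression, the unadjusted slope is multiplied by λ = 1 − (b × SD_CCT)²/SD_reading², and the standardised effect by √λ. For b = 0.04, SD_CCT 30 and SD_reading 6, λ = 1 − 1.44/36 = 0.96. With 50 per group, power that is 80% with adjustment becomes 78%. Over b 0.02-0.07, SD_CCT 30-40 and SD_reading 4-8, λ runs from 0.99 to 0.51 and power from 80% to 52%.

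**Continuous outcome** (as for MD or VFI, oriented so that higher means worse; N = 100, true standardised slope 0.285, b = 0.04, SD_CCT 35, SD_reading 6). With no direct CCT effect, the slope is 0.272 without CCT and 0.288 with it (power 77% and 79%). With thin-cornea risk of 0.15 SD per SD, 0.232 and 0.281 (62% and 78%). With the same risk for thick corneas, 0.304 and 0.286.

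**The case against.** The strongest case against has five parts.

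1. *The premise is not in the documents.* They list IOP and CCT as separate variables and never say that one shifts the other. This stands. The point is conditional on an assumed shift, shown over a range.
2. *The direction is not fixed.* A reader might infer that the plan understates the IOP effect. The documents do not support that: with thick corneas at higher risk, IOP alone is overstated. Towards the null is the result only if CCT is unrelated to progression or thin corneas carry risk.
3. *The pure instrument effect is small.* At 0.2-0.4 mmHg per 10 µm it costs a few hundredths of the OR and a few points of power at most. The large losses need either the steepest shift with a narrow IOP spread, or a direct CCT effect, which is ordinary confounding added to the reading error. This stands.
4. *If CCT matters, the rule will select it.* Partly true. With a direct effect of OR 1.7 per SD, CCT passes in about 90% of simulated cohorts. But the IOP t-test then has only 50% down to 13% power, so IOP itself may not reach the joint model.
5. *It is peripheral.* The SAP's regressions are aimed at the SNPs, and it states no IOP hypothesis. A reader might infer that the genetic results are affected. Distorted IOP would bias a SNP estimate only if genotype were related to IOP, which nothing here shows.

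**Conclusion.** The gap is real but conditional. The SAP does not pair inclusion IOP with CCT, and its entry rule is not designed to catch a variable that acts through another's reading. If applanation readings rise with CCT, the IOP association may be biased. Against a true OR of 1.5, the loss is slight at 0.2-0.4 mmHg per 10 µm and reaches about 1.39 at 0.7 when CCT is unrelated to progression. It is larger (to about 1.24) if thin corneas carry risk, and reversed (about 1.54-1.57) if thick corneas do. The joint model returns about 1.5 in all three cases, so the remedy does not depend on knowing the direction.

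The shift, the spreads, the cohort size and the CCT effect are all assumptions, and confidence in any particular size is low. This is an inexpensive improvement to the risk-factor analysis. It is not a threat to the SNP comparisons.

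**What to change.** Add to the SAP: whenever inclusion IOP is analysed as a risk factor or as a covariate for GPA, MD or VFI, CCT of the same eye is entered in the same model, whatever the univariate result for either. The IOP estimate is taken from that model, and the t-test of IOP between GPA groups is descriptive only.

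Cost: one SAP sentence and one degree of freedom. CCT is already recorded at inclusion, so no new data are needed. If CCT is irrelevant to both the reading and progression, about 1 percentage point of power is lost. If thick corneas carry the risk, apparent power for IOP also falls (79-85% to 71-74% in the runs above), but only because an upward bias has been removed. The change covers inclusion IOP only; the six-monthly readings would need their own rule if they are analysed.

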## Cover Page

Plan Statistical analysis

Project title: Genetic and risk factors in exfoliation glaucoma (Glaugene)

NCT: N.A.

Date of approval: 2012, May 6.

All statistical analyses will be performed using SPSS version 28.0.1.0 (IBM, [name]) software. Clinical characteristics of the cohort will be compared in relation to progression/no progression of glaucoma based on guided progression analysis (GPA). Categorical variables will be compared with Fisher's exact test while continuous variables with Student's t-test. The single nucleotide polymorphism (SNP) allele distribution between no progression and progression cases based on GPA will be compared using Fisher's exact test. The distribution of the haplotypes between no progression and progression cases based on GPA will be compared using Chi2 analyses within the Haplovie 4.1 software. The relation between the SNPs and progression/no progression in glaucoma will be tested using regression analyses (logistic or linear). In these analyses, mean deviation (MD) and visual field index (VFI), in addition to GPA, will be used as outcome variables measuring progression/no progression of glaucoma. Potential covariates will be first tested for association with the outcome variable (i.e., GPA, MD, and VFI) using univariate linear or logistic regression (depending on the character of the outcome variable). Associated variables will then be included as covariates in multivariate regression analyses. Finally, a regression analysis will be performed, including the genotypes of the two SNPs as predictors (both SNPs within the same model) and GPA/MD/VFI as outcome variables.

A power analysis based on Fisher's exact test will be performed using the Power and Sample Size Calculations software (<http://biostat.mc.vanderbilt.edu/PowerSampleSize>). Each SNP will be analysed separately. In all cases, the type I error ( $\alpha$  error) will be set to 0.05.

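### Student's t-test between outcome-defined groups does not hold 5% if both group sizes and SDs differ; Welch's test is a cheap improvement for the clinical-characteristics comparison only

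*SAP*

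**What the plan says.** The only text of the SAP, under its cover page, sets out the comparison: "Clinical characteristics of the cohort will be compared in relation to progression/no progression of glaucoma based on guided progression analysis (GPA"). Within it, Fisher's exact test is used for categorical variables, and the rest is "continuous variables with Student's t-test". The SAP mentions no variance check, unequal-variance form or rule for skewed variables.

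The error rate is common to all tests: "In all cases, the type I error" is one that "will be set to 0.05". Sidedness is not stated.

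No sample size, expected share of progressors or SD appears in either document. On power the SAP only announces a calculation, for a different test: "A power analysis based on Fisher's exact test will be performed using the Power and Sample Size Calculations software".

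The protocol's list of inclusion variables shows which continuous measures may enter. They include age, IOP, corneal thickness, visual acuity on a 0.1 to 1.0 scale, cup/disc ratio and the two visual field indices: "The MD measured in dB, and the VFI measured in" percent.

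**The concern.** The pooled t-test estimates one common variance. When the groups differ in size, that estimate is dominated by the larger group, while the true standard error is dominated by the smaller. If the smaller group is the more variable, the standard error is too small and the test rejects too often. If it is the less variable, the test rejects too rarely and power is lost.

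The design gives no protection on either count. The groups are defined by what happens to patients during follow-up, so their sizes cannot be balanced. Several measures are bounded or tied to disease severity (VFI, visual acuity, cup/disc ratio, MD). For these a shift in mean can bring a change in spread, so equal SDs should not be taken for granted.

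The project is titled "Genetic and risk factors in exfoliation glaucoma (Glaugene"), so readers may take this comparison as evidence on clinical risk factors. A continuous characteristic could then be declared different, or missed, because of the variance estimate and not because of the means.

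**Working it through.** **Inputs.** From the SAP: Student's t-test, groups by GPA, alpha 0.05. Assumed, because the documents do not give them: a two-sided test, the pooled form, the share *f* of patients in the smaller group, and the SD ratio *r* (smaller group over larger group). The larger group's SD is set to 1.

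**Formula.** Up to a common factor 1/N:

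- true variance of the mean difference: V_true = r²/f + 1/(1−f)
- variance the pooled test uses on average: V_pool = [f·r² + (1−f)]·[1/f + 1/(1−f)]
- large-sample type I error = 2·[1 − Φ(1.96·√(V_pool/V_true))]

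**Reproducing the plan's figure.** The only stated number is alpha = 0.05. With r = 1, V_pool = V_true for any split, and with f = 0.5 they are equal for any r. In both cases the formula returns 5.0%.

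**Worked example, 1:3 split (f = 0.25).**

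- r = 2: V_true = 16 + 1.333 = 17.333; V_pool = 1.75 × 5.333 = 9.333; 1.96·√0.538 = 1.438; error 15.0%.
- r = 0.5: V_true = 1 + 1.333 = 2.333; V_pool = 0.8125 × 5.333 = 4.333; 1.96·√1.857 = 2.671; error 0.8%.

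**Type I error (%) of the pooled test over the assumed range**

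| Split | r = 0.5 | 0.67 | 0.8 | 1 | 1.25 | 1.5 | 2 |
|---|---|---|---|---|---|---|---|
| 50:50 | 5.0 | 5.0 | 5.0 | 5.0 | 5.0 | 5.0 | 5.0 |
| 40:60 | 2.7 | 3.4 | 4.1 | 5.0 | 6.1 | 7.0 | 8.2 |
| 30:70 | 1.2 | 2.2 | 3.2 | 5.0 | 7.3 | 9.3 | 12.5 |
| 25:75 | 0.8 | 1.7 | 2.9 | 5.0 | 7.9 | 10.7 | 15.0 |
| 20:80 | 0.4 | 1.3 | 2.5 | 5.0 | 8.6 | 12.1 | 17.9 |

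Simulation with normal data agrees. At 30 v 90 the pooled test ran from about 0.7% or 0.8% (r = 0.5) to about 15% (r = 2).

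**Missed differences.** Take 30 v 90, r = 0.5 and a true difference of 0.4 SD of the larger group. The true standard error is √(0.25/30 + 1/90) = 0.139. The pooled test needs a difference of about 1.96·√(4.333/120) = 0.372, so power is Φ((0.400 − 0.372)/0.139), about 58%. Welch's test has power Φ(0.400/0.139 − 1.96), about 82%. Simulation gives 57% and 81%.

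**Welch's test, normal data.** Simulated type I error was 4.8% to 5.1% in every scenario (splits 50:50 to 20:80, 10 v 40 and 50 v 150; r from 0.5 to 2).

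**What Welch's test costs when SDs are equal.** Simulated power, with the effect chosen for a nominal 80%:

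| Groups | Pooled | Welch | Loss (points) |
|---|---|---|---|
| 50 v 50 | 79.2 | 79.2 | 0.0 |
| 30 v 70 | 79.2 | 78.7 | 0.5 |
| 25 v 75 | 79.3 | 78.2 | 1.1 |
| 20 v 80 | 79.3 | 77.3 | 2.0 |
| 10 v 40 | 78.3 | 73.6 | 4.7 |

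**Strong skewness (exponential data).** With r = 2, Welch's test ran at 7.0% (25 v 75), 7.4% (20 v 80) and 9.1% (10 v 40), against 15.6%, 18.3% and 18.5% for the pooled test. With equal SDs at 25 v 75, Welch's test was the worse of the two: 6.0% against 4.8%.

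**The covariate-selection step.** For GPA the SAP screens covariates by univariate logistic regression. At 30 v 90 with normal data, its likelihood-ratio test rejected at 1.0%, 5.1%, 10.8% and 15.1% for r = 0.5, 1, 1.5 and 2. A separate simulation gave 0.5% and 15.7% at the two extremes. The distortion is essentially that of the pooled t-test.

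**The case against.** The strongest reply is that the t-test has one job in this SAP, a comparison of clinical characteristics. Covariates are chosen by univariate regression and then adjusted for. The SNP questions use Fisher's exact test, a chi-squared analysis of haplotypes, and regression. No genetic or adjusted result therefore depends on the t-test. Changing it leaves the logistic screening step equally exposed, and the table and the regression could then disagree on the same variable. All of this stands, and it limits the gain.

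It is also fair that the documents support a 1.5- to 2-fold SD ratio no better than they support equal SDs, and that Welch's test is neither free in small groups nor a cure for skewness. Both points stand as limits on the size of the problem and on the remedy.

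The reply does not show that the pooled test is the better choice. When outcome-defined groups also differ in SD, it loses its stated error rate. With roughly normal data Welch's test keeps it, at a small cost in groups of moderate size.

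**Conclusion.** The point holds as a cheap improvement of minor severity. If group sizes and SDs both differ, the stated test does not run at 5%. At an assumed 1:3 split the error is about 2.9% to 7.9% for modest SD differences (ratio 0.8 to 1.25) and 0.8% to 15.0% for two-fold differences. The split and the SD ratios are assumptions; the plan gives neither.

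A reader might infer three stronger things that the documents do not support:

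- That unequal group sizes alone invalidate the test. They do not; with equal SDs it stays at 5.0% for every split.
- That the trial's error rate is 15%. That figure needs both a 1:3 split and a two-fold SD ratio, and nothing in the documents establishes either.
- That the SNP findings or the choice of covariates rest on this test. The SAP assigns both to other methods.

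**What to change.** In the sentence on continuous variables, replace Student's t-test with Welch's t-test (unequal variances), and report each mean difference with its 95% CI. This changes one phrase and uses the same SPSS procedure.

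The cost, if SDs are in fact equal, is up to 2 points of power at N = 100 for splits as uneven as 20:80, and nearly 5 points at 10 v 40. For strongly skewed variables the error rate may still be about 6% to 9%, so the change should not be presented as a complete remedy. Nor does it alter the univariate logistic regression for GPA. If the clinical table and that regression disagree on a variable, the report should show the group SDs so that the reason can be seen.
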